n=10 per group	99%	98%	95%	79%

n=15 per group	100%	100%	99%	90%
n=20 per group	100%	100%	100%	97%
Mean Diff(T2-T1) Group 1=0.0, Group 2=1.6				
$\alpha = 0.05$	Var(Time1)=Var(Time 2)=3.00		Var(Time1)=Var(Time 2)=6.00	
Sample Size	Empirical Power $\rho=0.70$	Empirical Power $\rho=0.50$	Empirical Power $\rho=0.70$	Empirical Power $\rho=0.50$
n=10 per group	72%	49%	45%	31%
n=15 per group	88%	68%	57%	40%

All primary and secondary outcomes will be visually assessed (boxplots, histograms, etc.) for normality and/or continuous data will be examined with a Shapiro-Wilk test. We will use a 2-way (group x time) mixed-model analysis of variance (ANOVA) to assess group interaction. Where significant interaction effects are observed, paired and independent t-tests will be used to determine significant differences within and between groups. Alpha will be set at < 5%.

11) Provisions to Monitor the Data to Ensure the Safety of Subjects

Please refer to the attached document DSMB 0719

12) Withdrawal of Subjects

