4. BMR
5. Thickness of epicardial adipose tissue as measured by echocardiography
6. Volumes of subcutaneous adipose tissue (SAT), visceral adipose tissue (VAT), intramuscular fat, (IMF) as measured by CT.

Secondary Study Endpoints

1. Lipid profiles
2. Lower extremity bone mineral density
3. hsCRP in adults

4. Proinflammatory adipokines: tumor necrosis factor- α , interleukin-6, monocyte chemoattractant protein-1, plasminogen-activator inhibitor-1, vascular cell adhesion molecule-1 and intercellular adhesion molecule-1
5. Anti-inflammatory adipokines: Adiponectin and Interleukin-10

7. Procedures Involved

Overview:

Primary outcome measures will include body composition by iDXA, CT, Echocardiography, insulin sensitivity, glucose effectiveness and BMR, while secondary outcomes will include lower extremity BMC and density, lipid profiles, hsCRP, fasting insulin, TNF α , IL-6, PAI-1, ICAM-1, VCAM-1 MCP-1, adiponectin and IL-10, Non-esterified free fatty acids determined before and after the 16-week interventions. Subjects will be randomly assigned (50% chance) to either HBFES LCE + Diet on an RT300 ergometer or Home-based (HB) Diet Alone intervention as determined by a random number generator.

Study Procedures include:

- **History and Physical Examination:** Each subject will undergo a complete history and physical examination by a physiatrist board certified in SCI medicine. This will include general demographics, past medical history, medications, family and social history, race and ethnicity. Subjects will undergo an AIS exam which is a system of tests used to define and describe the extent and severity of a patient's spinal cord injury. 28 key sensory points will be tested on each side of the body for light touch and pinprick sensations. There will also be a strength assessment of ten muscles on each side of the body. The subject will be graded based on their sensations and strength assessment. Subjects who have had a neurological physical exam with ASIA completed in the last year by a licensed physiatrist board certified, will not need a repeat exam. Women of childbearing potential will have a pregnancy test obtained.
- **ECG:** A resting 12-lead ECG will be performed on each subject to rule out any coronary artery disease.

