- **Surface Neurostimulation:** The physical exam will conclude with a surface neurostimulator trial to determine muscle response to electrical stimulation at bilateral gluteus maximus, hamstrings, vastus lateralis, and vastus medialis. If there is no muscle response, the patient may not be included in the study.
- **Dobutamine Echocardiogram/Epicardial Adipose Tissue**

- **Screening Labs:** A full electrolyte panel (fasting sodium, potassium, chloride, bicarbonate), BUN, creatine, glucose and HgbA1c will be drawn at the Clinical Translational Research Site, 7th floor during the IVGTT.
- **Blood labs**
 - **Blood Lipids, hsCRP and inflammatory panels:** Each subject will have lipid profiles (HDL-c, LDL-c, total cholesterol, and triglycerides). hsCRP, insulin, non-esterified free fatty acids, IL-6, TNF α , MCP-1, PAI-1, ICAM-1, VCAM-1, Adiponectin, IL-10 assessed before and after the 16-week intervention. Lipids and hsCRP will be determined by standard analyses procedures employed by the CRC. Secondary variables of particular note include HDL-c, total cholesterol:HDL-c ratio and hsCRP.
 - **Genetic Testing:** A separate sample will be collected and stored for future analysis to assess genetics in relation to body composition and metabolism after spinal cord injury.
- A total of approximately 26 ml of blood (approximately 5 teaspoons) will be collected for all the aforementioned tests.
- **Body Composition:** Dual Energy X-Ray Absorptiometry (DXA): Total body and regional (lumbarspine, proximal femur, and forearm) dual-energy x-ray absorptiometry (DXA) scans will be performed using a Lunar iDXA bone densitometer at the Lynn Rehabilitation Center Physical Medicine and Rehabilitation (Lynn PM&R) Research Lab. DXA scans will be completed at screening, baseline, and at the midpoint and end of the study intervention to assess for changes in body composition. All scans will be performed and analyzed by a trained, certified DXA operator. A single trained investigator will analyze all scans. The DXA total bone mineral content measurements will be used to correct for the mineral fraction in the criterion body composition model (4-compartment model) [39]. Anthropometric measures (skinfolds, girths and circumferences) will be obtained for pilot data using a CRC adjunct proposal. Primary variables will include %BF, Absolute Fat Mass (FM), and Absolute FFM determined by DXA.
- **Weight:** Subjects will be weighed at each visit to the Lynn PM&R Research Lab.

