- **Non-contrast CT images:** Abdominal/pelvic/thigh scans will be performed at UM/Sylvester Department of Radiology, these will be obtained pre and post intervention using a 128-slice multidimensional whole body scanner before and after the intervention. Prior to undergoing the scan subjects will have their lower extremities ranged and stretched as described above. Images will be attained from the xiphoid process to the superior aspect of the patella. All images will be analyzed at a separate workstation using TeraRecon iNtuition imaging software. Images are automatically segmented into adipose tissue, skeletal muscle, and bone/background based on location and then their attenuation properties, with adipose having the lowest attenuation and bone/background having the highest attenuation. A CT attenuation range of -120 to -40 Hounsfield units (HU) will be used to encompass abdominopelvic adipose tissue, -190 to -30 HU will be used for IMF, and -29 to +150 HU will be used for skeletal muscle (needed for IMF quantification).⁷¹ Cross sectional area (CSA; cm²) will be automatically calculated by the software by summing the pixels of the tissue and multiplying it by the pixel surface area for each adipose tissue depot, while volume (cm³) will be computed by multiplying the CSA by the image slice thickness and inter-slice space. Visual distinction will be used to determine VAT versus SAT based on the anatomical locations of the tissues and CSA and volumes will be summed together from consecutive slices. Total VAT mass and total SAT mass (in grams) will be the product of the total volume and fat density (0.9196 g/cm³). For the CSA of IMF, the outer perimeter of the thigh muscle group will be traced and the femur will be excluded. A bimodal graph will be used to determine pixel differences between muscle (higher attenuation) and IMF (lower attenuation). To account for muscle size, IMF CSA will be normalized to muscle CSA. Volume of IMF will be calculated as described above.

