- Methods: Each subject will undergo a complete physical examination by a physiatrist board certified in SCI medicine, with 12-lead resting ECG and dobutamine echocardiogram stress test (reviewed by the cardiologist) and comprehensive dietary assessment prior to participation. Echocardiograms (transthoracic two-dimensional guided M-mode) will be performed by standard techniques with subjects in the left lateral decubitus position. The thickness of EAT will be measured perpendicular to the free wall of the right ventricle at the end of systole in three cardiac cycles using parasternal long-axis or short-axis view. Echocardiographically, EAT is identified as the echo lucent (echo-free) space between the superficial/external wall of the myocardium and the visceral layer of the serous pericardium. Measurement of EAT on right ventricle was chosen for two reasons: 1) this point is recognized as the greatest absolute epicardial fat layer thickness, and 2) parasternal long-and short-axis views allow the most accurate measurement of epicardial adipose tissue on the right ventricle with optimal cursor beam orientation in each view. The baseline measurement of EAT will precede the dobutamine stress echocardiogram. The physical examination by [name] will conclude with a surface neurostimulator trial to determine muscle response to electrical stimulation at bilateral gluteus maximus, vastus lateralis, and vastus medialis. During this visit, participants will also be screened for total body fat percentage by DXA. Screening labs will be obtained including fasting sodium, potassium, chloride, bicarbonate, BUN, creatinine, glucose and HgbA1c. Within approximately, two weeks, depending on subjects' availability, eligible participants will return to the University of Miami medical campus. This visit will include the remaining DXA scans for estimation of body composition. After DXA completion, participants will be escorted to the UM Towers: Clinical Translational Research Site (CTRS), 7th floor and will be asked to remain in the CTRS overnight. At 6 am the following morning, the subject will be gently awakened for determination of basal metabolic rate (BMR) by indirect calorimetry using a canopy COSMED Quark RMR (Rome, Italy) gas exchange

IRB Study Number: 20190659

NCT03495986

Version v18 071825

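### Primary CT and echo fat endpoints include reader-judgement steps, and the plan does not mask the readers to arm or visit

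*Combined protocol and SAP*

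**What the plan says.** Section 6 lists EAT thickness by echocardiography as a primary endpoint, followed by "Volumes of subcutaneous adipose tissue (SAT), visceral adipose tissue (VAT), intramuscular fat, (IMF) as measured by CT". DXA body composition (percent fat, fat mass, fat-free mass) is also primary.

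Section 7 describes how each is read.

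- **CT, automated part.** "Images are automatically segmented into adipose tissue, skeletal muscle, and bone/background based on location" and then on attenuation. Hounsfield ranges are fixed by tissue, and the software computes cross-sectional area.
- **CT, judgement part.** "Visual distinction will be used to determine VAT versus SAT", by anatomical location. For IMF, "the outer perimeter of the thigh muscle group will be traced and the femur will be excluded". Analysis is done at a separate workstation with named software. The number of readers, any repeat reads and any masking are not stated.
- **EAT.** "The thickness of EAT will be measured perpendicular to the free wall of the right ventricle", at end-systole, over three cardiac cycles, from either of two parasternal views. No reader is specified.
- **DXA.** "A single trained investigator will analyze all scans". This sentence appears under Body Composition and again under lower-extremity bone density. It is not made for CT or echo.

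Randomization follows the baseline visit. Study staff deliver the ergometer to the home of each participant in the cycling arm and monitor the sessions remotely.

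**The concern.** When a person decides where a boundary lies, knowing which arm a scan belongs to, or whether it is the later scan, can influence the decision. The plan also states an expected direction. Section 3.2 expects the combined arm to lose body fat and improve glucose handling, and Section 3.3 expects diet alone to cost lean tissue. The arms (home cycling plus diet against diet alone) cannot be hidden from the staff who deliver them.

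At stake is the credibility of several primary endpoints. If readers know the arm, a between-group difference in VAT, IMF or EAT could partly reflect reading. If they know only the visit, pre/post change within each arm could be shifted, which matters for Objectives 1 and 2 and for the paired tests in Section 10. A larger sample does not remove either kind of bias.

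**Working it through.** **Step 1: where judgement enters.** The plan has no figure to reproduce here, because it gives no effect size, SD, reader error or power for any CT or EAT endpoint. The check is a reading of Section 7.

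| Endpoint | Automated or fixed | Left to a reader | Readers stated | Masking stated |
|---|---|---|---|---|
| VAT, SAT | Segmentation, -120 to -40 HU, area | VAT/SAT split | No | No |
| IMF | Segmentation, -190 to -30 HU (muscle -29 to +150 HU), area | Thigh muscle perimeter | No | No |
| EAT | Site, angle, end-systole, three cycles | View and thickness | No | No |
| DXA | Device and software | Analysis step, not detailed | One | No |

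A single attenuation window covers all abdominopelvic fat, so it cannot separate VAT from SAT. Automation finds the fat, and the reader assigns it to a depot. For IMF, the traced perimeter determines which thigh fat is counted.

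**Step 2: what a reader could know.** Baseline CT precedes randomization, but the plan does not say when it is read. The post-intervention CT always follows allocation. No available text hides arm or time point at reading.

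**Step 3: which comparison is exposed.** A shift tied to visit alone falls on both arms. It enters each within-group change and largely cancels in the between-group difference. A spurious between-group difference requires knowledge of arm.

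**Step 4: scale, under assumptions.** Section 10 describes its change-score regression as equivalent to a two-sample t-test. That test reproduces the plan's %BF power at 20 per group to within one point. The difference is (31.8 − 28.5) − 0.06 = 3.24, and the SD of change is √(2 × Var × (1 − ρ)). The results are 99.9%, 97.9%, 95.4% and 80.6%, against the stated 100%, 97%, 95% and 80%. This checks the test only; it says nothing about CT.

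Now set the true effect to zero and assume a between-arm reading bias of *b* SDs of change. The noncentrality is *b*√(n/2), with 2n − 2 degrees of freedom and two-sided alpha 0.05. Section 10's 15% dropout gives 20 × 0.85 = 17 per arm.

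| Assumed *b* | Noncentrality, n = 20 | False positives, n = 20 | Noncentrality, n = 17 | False positives, n = 17 |
|---|---|---|---|---|
| 0 | 0 | 5% | 0 | 5% |
| 0.10 | 0.32 | 6.1% | 0.29 | 5.9% |
| 0.25 | 0.79 | 12.0% | 0.73 | 10.9% |
| 0.50 | 1.58 | 33.8% | 1.46 | 29.3% |
| 0.75 | 2.37 | 63.7% | 2.19 | 56.4% |

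The values of *b* are not estimates. At a given *b*, the larger sample has the higher false-positive rate.

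**The case against.** The best counter-argument is that Section 7 already limits discretion. CT segmentation, Hounsfield limits and area calculation are automated, and the EAT site, angle and cardiac phase are fixed. Section 10 names percent body fat and insulin sensitivity as the most important variables and sizes the trial on them. Insulin sensitivity comes from a model fit, and no judgement step is described for percent fat. Silence about masking does not prove that readers are unmasked.

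Much of this stands, and it rules out several stronger readings that a reader might infer.

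- *One reader determines the CT results.* The single-investigator sentence belongs to DXA. For CT and EAT the number of readers is unstated.
- *The endpoints rest wholly on judgement.* They do not. Judgement enters at the depot split, the thigh perimeter and the EAT measurement.
- *A given percentage shift in traced area becomes the same percentage treatment difference.* Tracing is described only for IMF, where fat pixels inside the perimeter are counted and normalised to muscle area. VAT is not described as traced.
- *Knowing the visit creates a treatment effect.* That mainly affects within-group change.

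The objection does not remove the gap. The judgement steps decide which depot the fat is assigned to, those depots are primary endpoints, and nothing in the plan prevents a reader from knowing arm and visit.

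**Conclusion.** The point holds as a gap in outcome assessment that should be closed. Several primary endpoints contain a human decision, and the plan as written allows it to be made with knowledge of arm and visit. It does not show that bias will occur or that any one person controls the result.

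The size cannot be derived from the documents. If the between-arm reading bias were as small as 0.1 SD of change, the false-positive rate would barely move (6.1% at 20 per arm). At 0.5 SD it would be about one in three (33.8%). These figures assume a zero true effect, a constant bias and a t-test on change scores.

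The conclusion also rests on the available text. Part of the text around Section 17 is not included, and Section 11 refers to a separate monitoring document. A masking statement in either would answer the point.

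**What to change.** Add one paragraph to Section 7, covering the CT, DXA and EAT descriptions.

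1. State how many people read each modality.
2. Have the existing reader(s) for each modality perform outcome reads on files relabelled with random codes that hide arm and visit. Section 23 describes coded subject IDs, but a subject code alone does not hide the visit, so each image needs its own code.
3. Read each subject's scans together in random order: pre and post for CT and EAT; baseline, midpoint and end for DXA.
4. Keep the eligibility DXA and safety echo reads immediate. If the screening total-body DXA also supplies the baseline value, re-analyse it within the masked set.
5. Store the echo images so that EAT can be measured later from coded files.

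No extra scan, visit or reader is needed. The costs are that outcome reads wait until the post-intervention images exist, the coordinator must relabel files and hold the key, and echo images must be retained. Masking acts at reading, so it can still be applied to images already acquired if they have been kept. It does not mask acquisition.

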- **Stress Test & Energy Expenditure:** This procedure will be performed on all subjects at the UMH Echocardiography Laboratory under the supervision of [name]. A dobutamine echocardiogram stress test will be performed prior to exercise to rule out significant cardiovascular disease and to establish peak heart rate that will be used to prescribe peak exercise intensity for the HBFES exercise intervention as per ACSM guidelines; this is a standard procedure at our SCI Center for persons desiring exercise. Before the administration of the dobutamine, epicardial adipose tissue will be measured. A post-intervention echocardiogram will also be performed to measure epicardial adipose tissue following the intervention [109]. The COSMED Quark RMR (Rome, Italy) gas

exchange measurement system will be used with canopy to determine basal metabolic rate (BMR) as described above, and exercise energy expenditure by mask indirect calorimetry during the aerobic exercise (in target heart rate zone) for exercise sessions 1, 41 and 80. BMR will be utilized to assess caloric needs for the dietary intervention proposed. Primary variables will include BMR and exercise energy expenditure.

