lengthening bouts until at least continuous 40-minute sessions are tolerated. However, subjects will have the flexibility to advance through the accommodation period at their own pace, as tolerated. Exercise intensity during the remaining 12-week intervention will be set at 70% maximal heart rate (HRmax), as determined by the initial dobutamine stress test, or as close to that as tolerated / capable by the subject based on stimulation intensity and resistance (see below). Exercise training will consist of three to five, 40-67-minute sessions (200 minutes at target intensity) each week for a total of 16 weeks; 10-minute warm-up and cool-down sessions will accompany each exercise session. An intent-to-treat protocol will be employed, and thus all subjects randomized will be used in the final data analyses. FES leg cycle ergometry (LCE) training will be induced on the RT300 FES-LCE ergometer (Restorative Therapeutics, Inc., Baltimore, MD) through wires connected to silastic surface electrodes over bilateral quadriceps, hamstring and gluteal muscles. Electrodes will be placed on the skin of the following corresponding skeletal muscle groups. Quadriceps: One electrode will be placed on the skin approximately 3 finger widths above the superior aspect of the patella, and the other 4-5 finger widths from the inguinal crease. The Q-angle should be kept in mind when centering the electrodes over the quadriceps. Hamstrings: One electrode will be placed 2-3 finger widths above the popliteal fossa and the other electrode approximately 1 hand width apart but no further than 3-4 finger widths from the gluteal fold. Gluteus Maximus: Two electrodes will be placed parallel and on the bulk of the muscle belly with at least 2 finger widths between electrodes. The medial electrode will be placed approximately 2-3 finger widths from and parallel to the gluteal cleft and the lateral electrode approximately 2-3 finger widths posterior to the greater trochanter. The above are guidelines and due to anatomical differences among subjects, slight modifications may be required at the discretion of the Physical Therapist in order to achieve optimal tetanic contraction. Subjects will be provided with a pictorial instructional guide on proper electrode placement. (FES Protocol for Patient and Families Appendix 6).

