- The RT300 FES-LCE computer sequences functional electrical stimulation impulses which induce contractions of the quadriceps, hamstrings, and gluteal muscles in an order that allows for the hip, knee, and ankle joints to combine to create the repetitive circular motion of pedaling. The RT300 has HIPAA Compliant internet connectivity that allows clinicians to follow results and make alterations to the exercise and cycle parameters remotely. Once a session is completed the performance data including time, distance, power, energy expenditure and the session parameters such as current amplitude, pulse width, current frequency, cycling speed and resistance are displayed and stored. The HIPAA compliant internet connectivity allows for the optimization of training and safety. The RT300 also allows the participant to cycle from his or her own wheelchair eliminating the need to transfer onto a cycle. Prior to starting home based FES-LCE, subjects will undergo 1-3 FES-LCE sessions in the Lynn PM&R Research Lab so that electrode application, ergometer function can be taught, and heart rate, blood pressure and possible autonomic dysreflexia symptoms could be monitored. A baseline blood pressure and heart rate reading will be obtained prior to beginning an exercise session and then every 10 minutes thereafter (for a total of three readings) while monitoring for symptoms of autonomic dysreflexia. Subjects will continue to be assessed for symptoms of autonomic dysreflexia during the session. After completion of the laboratory trial without incident, the subject will be cleared to begin home based FES-LCE. The PT and at least one other member of the research team will assist with delivery and set-up of the RT300 ergometer, cardiovascular monitoring and audiovisual teleconference equipment in the subject's home. The initial 1-2 sessions in-home will be monitored by in-person PT and/or RN, as well as by telemonitoring by research coordinator / graduate student in the lab and dietician on the CRC to ensure real-time audiovisual communication is intact. At any time during the 16-week intervention, should audiovisual monitoring equipment malfunction, telephone or Zoom communication initiated by a UM study team member) will allow for immediate home-evaluation of equipment by PT, RN and/or technicians. Study team members and participants will be protected from COVID-19 by observing standard precautions as is the practice when at the Lynn PM&R Lab. These include mask-wearing, handwashing, the use of sanitizer and/or sanitizing wipes, additionally social distancing to the extent possible. All subjects will be

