
asked to participate in 3-5 cycling sessions per week of 40-67 minutes for a total of 200 minutes/week in target intensity zone, plus 10-minute warm-up and 10- minute cool-down. Sessions will be monitored by the research staff via internet connection and telemedicine VitelNet and web cam (HR & BP q 10 minutes). Cycle parameters will be individualized depending on the amount of current needed to perform the cycling activity and depending on the comfort of the participants. The cycling parameter ranges will include maximum values not to exceed the following: 140 mA for current amplitude, 500 μ s for pulse width, and 100 Hz for frequency. Speed will be advanced between 30 and 50 rpm with an initial resistance of 0.5 Nm. The resistance will be set on automatic so that the RT300 cycle would vary the resistance to allow the set speed. For example, if the speed is set at 40 rpm and the resistance is at 1.0 Nm, if the participant cannot sustain the set speed at that resistance, the cycling system will automatically decrease the resistance to allow the participant to maintain the selected speed. Cycling duration will be increased over the 16-week period until a goal of between 40 and 67 minutes of continuous active FES cycling was attained. Subject and home assistants will be provided training concerning the placement of electrodes and the FES-LCE procedures. Medical guidelines proposed by Phillips will be employed at all sessions. [62]

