Once the subject has completed the screening visit and their eligibility for continued participation has been confirmed, they will be asked to return for a baseline assessment. At this visit, subjects will undergo the following procedures:

- Anthropometric measures performed at Lynn PM&R Research Lab)
- Remaining DXA scans (performed at Lynn PM&R Research Lab)
- CT (Abdomen/pelvis/thigh performed at UM/Sylvester Department of Radiology)
- BMR (following an overnight stay at CTRS)
 - A registered nurse will be available to stay with the subject during the overnight stay. A family member or caretaker will also be allowed to stay overnight.
- IVGTT (performed at CTRS)
A full electrolyte panel will be obtained (fasting sodium, potassium, chloride, bicarbonate), BUN, creatine, glucose and HgbA1c (performed at CTRS). Blood Lipids, hsCRP insulin, non-esterified free fatty acids, IL-6, TNF α , MCP-1, PAI-1, ICAM-1, VCAM-1, adiponectin, IL-10 and a separate blood sample for genetic analysis (performed at CTRS) will also be obtained. This process is expected to take approximately 18 hours to complete and will require an overnight stay at the CTRS. This visit can be arranged at the subject's convenience but must be scheduled within 2 weeks of the Screening Visit.
- COVID-19 PCR testing with a negative result within 48 of admission to CTRS for subjects and their caregiver if applicable

Randomization

Directly after the baseline visit subjects will be randomly assigned to the HBFES LCE + Diet or Diet alone intervention groups using a random number generator.

Exercise Trial and Mask Indirect Calorimetry Session 1: (Week 4)

HBFES LCE + Diet subjects will undergo at least 1 FES-LCE session in the Lynn PM&R Research Lab this week so that heart rate, blood pressure and possible autonomic dysreflexia symptoms can be monitored. Subjects' energy expenditure during aerobic exercise will be measured at this time by mask indirect calorimetry. This assessment represents Session 1 of the intervention. If another session is required, the subject will return within 5 days to perform another FESLCE session. After completion of the laboratory trial without incident, the subject will be cleared to begin home based FES-LCE.

Accommodation Period (Weeks 5-8)

The FES-LCE subjects will have an accommodation period of 4 weeks, during which four 10-minute exercise bouts/day will be interspersed with 5 minutes of rest, gradually

IRB Study Number: 20190659

NCT03495986

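### The laboratory cycling session that clears a C4-T4 subject for home use schedules only three blood pressure and heart rate readings, so a session longer than 20 to 30 minutes would end without a scheduled reading (minor)

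*Combined protocol and SAP*

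**What the plan says.** All of the text is in section 7, Procedures Involved, of the combined protocol and SAP.

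- **Purpose of the visit.** Under the Week 4 heading (Exercise Trial and Mask Indirect Calorimetry Session 1), the laboratory session is held "so that heart rate, blood pressure and possible autonomic dysreflexia symptoms can be monitored".
- **Reading schedule.** Under Exercise Training Intervention, a reading of blood pressure and heart rate is taken before exercise, "then every 10 minutes thereafter (for a total of three readings) while monitoring for symptoms of autonomic dysreflexia".
- **After the scheduled readings.** The next sentence names symptoms only: "Subjects will continue to be assessed for symptoms of autonomic dysreflexia during the session".
- **Clearance.** "After completion of the laboratory trial without incident, the subject will be cleared to begin home based FES-LCE". The visible text gives no blood pressure value that defines an incident and names no end-of-session reading.
- **Remotely monitored sessions.** These are followed by internet connection, telemedicine and "web cam (HR & BP q 10 minutes"). No maximum number of readings is given.

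The length of the laboratory session is not stated anywhere in the documents.

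**The concern.** Blood pressure is one of the stated purposes of this session, yet its schedule ends after a fixed count while symptom checks run on. The session is also the gate to unsupervised-site exercise in people with C4-T4 injury. Section 3.2 (Novel Home Based FES) says that earlier studies left out high injuries partly because of concern about autonomic dysreflexia, and section 13 accepts that dysreflexia may occur during stimulation.

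If the session outlasts the third reading, a rise in blood pressure without symptoms, late in exercise or during cool-down, would not be picked up by any scheduled measurement before clearance. Scheduled readings at the supervised gate could then stop sooner than they do in the home sessions that the gate permits. Heart rate is probably followed in any case to confirm the target zone, so blood pressure is the measurement that matters here.

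**Working it through.** **Inputs from the documents.** Baseline reading at minute 0, interval 10 minutes, total three readings (section 7, Exercise Training Intervention). The uncapped comparison is the same 10-minute interval, as used for remotely monitored sessions.

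**Last scheduled reading.** The wording allows two readings.
- A, baseline is one of the three: minutes 0, 10, 20. Last at minute 20.
- B, three readings after baseline: minutes 0, 10, 20, 30. Last at minute 30.

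**Uncapped schedule for a session of L minutes.** Number of readings = floor(L/10) + 1, with the last at 10 × floor(L/10). Readings lost to the limit = uncapped number − 3 (A) or − 4 (B), and never below 0. Minutes no longer covered = 10 × floor(L/10) − 20 (A) or − 30 (B), and never below 0.

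| Assumed L (min) | Uncapped readings (last at) | Lost, A / B | Minutes not covered, A / B | Share of session, A / B |
|---|---|---|---|---|
| 20 | 3 (20) | 0 / 0 | 0 / 0 | 0% / 0% |
| 30 | 4 (30) | 1 / 0 | 10 / 0 | 33% / 0% |
| 40 | 5 (40) | 2 / 1 | 20 / 10 | 50% / 25% |
| 55 | 6 (50) | 3 / 2 | 30 / 20 | 55% / 36% |

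For example, at 55 minutes under A: 6 − 3 = 3 readings, 50 − 20 = 30 minutes, 30/55 = 55%.

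**How long is the session likely to be?** Every length in the table is an assumption. Three statements point beyond 20 minutes without proving it:
1. The visit counts as training: "This assessment represents Session 1 of the intervention".
2. Energy expenditure is measured "during the aerobic exercise (in target heart rate zone) for exercise sessions 1, 41 and 80", so some work in the zone is expected at this visit.
3. "10-minute warm-up and cool-down sessions will accompany each exercise session". If that covers this visit, warm-up and cool-down alone take 10 + 10 = 20 minutes. Ten minutes of work then makes 30, and twenty makes 40.

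The 55-minute row matches the accommodation format, 4 × 10 minutes of cycling + 3 × 5 minutes of rest = 55. The protocol places that format in Weeks 5-8, after this visit, so carrying it back to Session 1 is a further assumption and the row should be read as an upper illustration.

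**The case against.** The strongest reply is that there may be no gap. Three readings at 10-minute spacing may simply describe a session of 20 to 30 minutes. That would suit a teaching visit for a novice, held before the accommodation weeks in which subjects still cycle in 10-minute bouts. This stands: the documents do not settle the length, and the point has to stay conditional.

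The second reply is that the text sets a schedule and does not forbid further readings. Section 13 says that dysreflexia will be closely watched for and stimulation reduced or stopped if it does not resolve. This also stands. A reader might infer that blood pressure goes unmeasured after the third reading, or that subjects are cleared unsafely. The documents do not support either inference. They show only that no later reading is scheduled.

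The third reply is that other safeguards cover the risk. A physical therapist and/or nurse attends the first one or two home sessions, and remotely monitored sessions have uncapped readings. Uncontrolled dysreflexia and its potential causes are grounds for exclusion (section 4), and recurrence leads to removal (section 12.1). The medical guidelines cited for all sessions, the patient FES protocol (Appendix 6) and the attached DSMB document are not visible and may already govern blood pressure here. These reduce the risk considerably. They do not fully answer the point, because the home safeguards act after clearance, stopping and removal depend on detection, and the exclusions cannot anticipate a first response to stimulation.

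Finally, counts of cuff readings are not a measure of harm. The documents give no frequency for a symptomless rise that first appears after minute 20 or 30, so no risk estimate is possible.

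**Conclusion.** The point holds as a minor, optional improvement. The plan states a limit of three readings at the session that clears a subject for home use, names only symptom checks after it, and sets a fuller standard for remotely monitored sessions. The cost of the limit is 0 to 3 scheduled readings per session at assumed lengths of 20 to 55 minutes. It is zero at 20 minutes, and zero at 30 minutes if baseline is extra.

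The conclusion rests on two things that the documents leave open: that the session runs past the last scheduled reading, and that no unseen guideline already requires more. Its benefit also depends on how many subjects still have to be cleared. Section 5 anticipates enrolment ending on December 31, 2024, and section 21 gives December 2022, while this version is stamped 071825. Those dates are anticipated, so open enrolment cannot be excluded, but few or no clearing sessions may remain.

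It would be wrong to infer any consequence for the endpoints, the sample size or the analysis. There is none.

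**What to change.** In section 7, delete the parenthetical limit on the number of readings. State that blood pressure and heart rate are read every 10 minutes to the end of the laboratory session, cool-down included, and that the investigator reviews all readings as well as symptoms before clearing the subject. Because the visible text gives no blood pressure value for an incident, the added readings would inform that judgement and would not act as an automatic stopping rule.

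The cost is one deleted phrase and one added sentence in an amendment, plus 0 to 3 cuff readings per session at the assumed lengths, taken by staff already in the room. If the session in fact lasts 20 minutes, or no subject remains to be cleared, the change brings no benefit.
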